8. SAFETY AND REPORTING

All Serious Adverse Events (SAEs) that occur following the subject's written consent to participate in the study through 100 days of last dose of study treatment must be reported to BMS Worldwide Safety, whether related or not related to study drug. If applicable, SAEs must be collected that relate to any later protocol-specified procedure (e.g., a follow-up skin biopsy). Hospitalizations and/or death related solely to progression of the underlying disease will not be considered an SAE.

Following the subject's written consent to participate in the study, all SAEs, whether related or not related to study drug, are collected, including those thought to be associated with protocol-specified procedures. The investigator should report any SAE occurring after these aforementioned time periods, which is believed to be related to study drug or protocol-specified procedure.

An SAE report should be completed for any event where doubt exists regarding its seriousness;

If the investigator believes that an SAE is not related to study drug, but is potentially related to the conditions of the study (such as withdrawal of previous therapy or a complication of a study procedure), the relationship should be specified in the narrative section of the SAE Report Form.

An appropriate SAE form (e.g. ex-US = CIOMS form or USA = Medwatch form) should be used to report SAEs to BMS. The BMS protocol ID number must be included on whatever form is submitted by the Sponsor/Investigator.

- The CIOMS form is available at: <http://www.cioms.ch/index.php/cioms-form-i>
- The MedWatch form is available at:
<https://www.fda.gov/downloads/AboutFDA/ReportsManualsForms/Forms/UCM048334.pdf>
- [name]
- In accordance with local regulations, BMS will notify investigators of all reported SAEs that are suspected (related to the investigational product) and unexpected (i.e., not previously described in the IB). An event meeting these criteria is termed a Suspected, Unexpected Serious Adverse Reaction (SUSAR). Investigator notification of these events will be in the form of a SUSAR Report.

- Other important findings which may be reported by BMS as an Expedited Safety Report (ESR) include: increased frequency of a clinically significant expected SAE, an SAE considered associated with study procedures that could modify the conduct of the study, lack of efficacy that poses significant hazard to study subjects, clinically significant safety finding from a nonclinical (e.g., animal) study, important safety recommendations from a study data monitoring committee, or sponsor decision to end or temporarily halt a clinical study for safety reasons.
- Upon receiving an ESR from BMS, the investigator must review and retain the ESR with the IB. Where required by local regulations or when there is a central IRB/IEC for the study, the sponsor will submit the ESR to the appropriate IRB/IEC. The investigator and IRB/IEC will determine if the informed consent requires revision. The investigator should also comply with the IRB/IEC procedures for reporting any other safety information.
- In addition to the Sponsor Investigator's responsibility to report events to their local HA, suspected serious adverse reactions (whether expected or unexpected) shall be reported by BMS to the relevant competent health authorities in all concerned countries according to local regulations (either as expedited and/or in aggregate reports).

SAEs, whether related or not related to study drug, and pregnancies must be reported to BMS within 24 hours. SAEs must be recorded on either CIOMS or MedWatch form & pregnancies must be reported on a Pregnancy Surveillance Form or can be submitted on the aforementioned SAE form to BMS.

SAE Email Address: [contact]

SAE [contact]

If only limited information is initially available, follow-up reports are required. (Note: Follow-up SAE reports should include the same investigator term(s) initially reported.)

If an ongoing SAE changes in its intensity or relationship to study drug or if new information becomes available, a follow-up SAE report should be sent within 24 hours to BMS (or designee) using the same procedure used for transmitting the initial SAE report.

All SAEs should be followed to resolution or stabilization.

8.1 DEFINITIONS FOR SERIOUS ADVERSE EVENTS

A **Serious Adverse Event (SAE)** is any untoward medical occurrence that at any dose:

- results in death
- is life-threatening (defined as an event in which the participant was at risk of death at the time of the event; it does not refer to an event which hypothetically might have caused death if it were more severe)

- requires inpatient hospitalization or causes prolongation of existing hospitalization (see **NOTE** below)
- results in persistent or significant disability/incapacity
- is a congenital anomaly/birth defect
- is an important medical event (defined as a medical event(s) that may not be immediately life-threatening or result in death or hospitalization but, based upon appropriate medical and scientific judgment, may jeopardize the subject or may require intervention [e.g., medical, surgical] to prevent one of the other serious outcomes listed in the definition above.)
Examples of such events include, but are not limited to, intensive treatment in an emergency room or at home for allergic bronchospasm; blood dyscrasias or convulsions that do not result in hospitalization.)
- Suspected transmission of an infectious agent (e.g., pathogenic or nonpathogenic) via the study drug is an SAE.

Although pregnancy, overdose, potential drug-induced liver injury (DILI), and cancer are not always serious by regulatory definition, these events must be handled as SAEs.

Any component of a study endpoint that is considered related to study therapy should be reported as an SAE (e.g., death is an endpoint, if death occurred due to anaphylaxis, anaphylaxis must be reported). Hospitalizations and/or death related solely to progression of the underlying disease will not be considered an SAE.

NOTE: (PI determines if this information regarding hospitalizations are considered SAEs and should be included in the protocol. This is supplemental information that is included in BMS-sponsored trials)

The following hospitalizations are not considered SAEs in BMS clinical studies:

- a visit to the emergency room or other hospital department < 24 hours, that does not result in admission (unless considered an important medical or life-threatening event)
- elective surgery, planned prior to signing consent
- admissions as per protocol for a planned medical/surgical procedure
- routine health assessment requiring admission for baseline/trending of health status (e.g., routine colonoscopy)
- Medical/surgical admission other than to remedy ill health and planned prior to entry into the study. Appropriate documentation is required in these cases.
- Admission encountered for another life circumstance that carries no bearing on health status and requires no medical/surgical intervention (e.g., lack of housing, economic inadequacy, caregiver respite, family circumstances, administrative reason).
- Admission for administration of anticancer therapy in the absence of any other SAEs (applies to oncology protocols)

- Hospitalizations and/or death related solely to progression of the underlying disease will not be considered an SAE.

8.2 ADVERSE EVENTS

An Adverse Event (AE) is defined as any new untoward medical occurrence or worsening of a preexisting medical condition in a clinical investigation participant administered study drug and that does not necessarily have a causal relationship with this treatment. An AE can therefore be any unfavorable and unintended sign (such as an abnormal laboratory finding), symptom, or disease temporally associated with the use of investigational product, whether or not considered related to the investigational product.

The causal relationship to study drug is determined by a physician and should be used to assess all adverse events (AE). The causal relationship can be one of the following:

Related: There is a reasonable causal relationship between study drug administration and the AE.

Not related: There is not a reasonable causal relationship between study drug administration and the AE.

The term "reasonable causal relationship" means there is evidence to suggest a causal relationship.

Adverse events can be spontaneously reported or elicited during open-ended questioning, examination, or evaluation of a subject. (In order to prevent reporting bias, subjects should not be questioned regarding the specific occurrence of one or more AEs.)

8.3 NONSERIOUS ADVERSE EVENT

- Non-serious Adverse Events (AE) are to be provided to BMS in aggregate via interim or final study reports as specified in the agreement or, if a regulatory requirement [e.g., IND US trial] as part of an annual reporting requirement.
- Non-serious AE information should also be collected from the start of a placebo lead-in period or other observational period intended to establish a baseline status for the subjects.

A ***non-serious adverse event*** is an AE not classified as serious.

Non-serious Adverse Event Collection and Reporting

The collection of non-serious AE information should begin at initiation of study drug. All non-serious adverse events (not only those deemed to be treatment-related) should be collected

continuously during the treatment period and for a minimum of 100 days following the last dose of study treatment.

Non-serious AEs should be followed to resolution or stabilization, or reported as SAEs if they become serious. Follow-up is also required for non-serious AEs that cause interruption or discontinuation of study drug and for those present at the end of study treatment as appropriate.

Laboratory Test Abnormalities

All laboratory test results captured as part of the study should be recorded following institutional procedures. Test results that constitute SAEs should be documented and reported to BMS as such.

The following laboratory abnormalities should be documented and reported appropriately:

- any laboratory test result that is clinically significant or meets the definition of an SAE
- any laboratory abnormality that required the participant to have study drug discontinued or interrupted
- any laboratory abnormality that required the subject to receive specific corrective therapy.

It is expected that wherever possible, the clinical rather than laboratory term would be used by the reporting investigator (e.g., anemia versus low hemoglobin value).

Potential Drug Induced Liver Injury (DILI)

Specific criteria for identifying potential DILI have not been identified for this protocol. Standard medical practice in identifying and monitoring hepatic issues should be followed.

Wherever possible, timely confirmation of initial liver-related laboratory abnormalities should occur prior to the reporting of a potential DILI event. All occurrences of potential DILIs, meeting the defined criteria, must be reported as SAEs.

Potential drug induced liver injury is defined as:

- 1) ALT (ALT or AST) elevation > 3 times upper limit of normal (ULN)
AND
- 2) Total bilirubin > 2 times ULN, without initial findings of cholestasis (elevated serum alkaline phosphatase)
AND
- 3) No other immediately apparent possible causes of ALT elevation and hyperbilirubinemia, including, but not limited to, viral hepatitis, pre-existing chronic or acute liver disease, or the administration of other drug(s) known to be hepatotoxic.

Wherever possible, timely confirmation of initial liver-related laboratory abnormalities should occur prior to the reporting of a potential DILI event. All occurrences of potential DILIs, meeting the defined criteria, must be reported as SAEs.

Pregnancy

If, following initiation of the investigational product, it is subsequently discovered that a study participant is pregnant or may have been pregnant at the time of investigational product exposure, including during at least 5 half-lives after product administration, the investigational product will be permanently discontinued in an appropriate manner (e.g., dose tapering if necessary for participant).

The investigator must immediately notify [contact] of this event via either the CIOMS, MedWatch or appropriate Pregnancy Surveillance Form in accordance with SAE reporting procedures.

Protocol-required procedures for study discontinuation and follow-up must be performed on the participant.

Follow-up information regarding the course of the pregnancy, including perinatal and neonatal outcome and, where applicable, offspring information must be reported on the CIOMS, MedWatch or appropriate Pregnancy Surveillance Form. A BMS Pregnancy Surveillance Form may be provided upon request.

Any pregnancy that occurs in a female partner of a male study participant should be reported to BMS. Information on this pregnancy will be collected on the Pregnancy Surveillance Form. In order for Sponsor or designee to collect any pregnancy surveillance information from the female partner, the female partner must sign an informed consent form for disclosure of this information.

Overdose

An overdose is defined as the accidental or intentional administration of any dose of a product that is considered both excessive and medically important. All occurrences of overdose must be reported as an SAE.

Other Safety Considerations

Any significant worsening noted during interim or final physical examinations, electrocardiograms, X-rays, and any other potential safety assessments, whether or not these procedures are required by the protocol, should also be recorded as a non-serious or serious AE, as appropriate, and reported accordingly.

8.4 STUDY STOPPING RULE

In keeping with the study primary endpoint, a stopping rule will be implemented in the unlikely event that the combination under study is deemed to have unacceptably high toxicities. Enrollment will be halted if more than 3 patients experience a Grade 4 or higher drug related toxicity (CTCAE v. 5) during the trial treatment period or up to 30 days after the last investigational drug infusion. The likelihood of observing more than 3 Grade 4+ drug-related adverse events is 80% if the true

rate is 20% and the likelihood is 91% if the true rate is 25%. This rule has an 83% chance of prematurely discontinuing trial enrollment after the 1st 10 patients are enrolled if the true rate of Grade 4 drug related toxicity is 40%. The study will be reviewed by the University of Washington/Fred Hutch Cancer Consortium Data and Safety Monitoring Committee (DSMC

STATISTICAL CONSIDERATIONS

All patients enrolled in the study, including those in the run-in phase will be included in the analysis of toxicity and efficacy.

Safety and tolerability is the primary endpoint of this study, and all patients enrolled will be assessed for this endpoint. Adverse events will be recorded and graded based on CTCAE v. 5, and their relationship to the experimental agents reported.

Similarly, all patients enrolled in the study (i.e., the initial 6 patient cohort, and the additional 14 patient expansion) will be included in the efficacy analyses. Clinical responses to the combination of nivolumab, ipilimumab and hypofractionated radiation will be based on RECIST 1.1 criteria. Oncologic outcome endpoints such as progression free and overall survival will be calculated from the date of study enrollment, until disease progression or death from any cause, respectively. Survival estimates will be calculated using the Kaplan-Meier method.

Exploratory endpoints of this study include correlative work performed on research serum and tissue samples.

Sample size determination

There are multiple ongoing studies in various tumor types exploring the activity of nivolumab and ipilimumab. In a published report of the combination in patients with advanced NSCLC treated on a phase I study (Checkmate, 012), treatment related serious adverse events were observed in 28% of patients (Hellmann Lancet Oncol 2017). This study plans to accrue 20 patients, a sample size that would allow us to estimate grade 3 or higher acute drug related toxicity rate of 30% with a confidence interval of 20% (95% confidence level) or an upper bound of 50%. This would allow us to reasonably exclude a clinically significant increase in toxicity with the addition of radiation therapy to the nivolumab and ipilimumab combination as defined by the upper bound of the confidence interval.

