2. STUDY OBJECTIVES

2.1 Primary Objective:

To demonstrate that nivolumab, ipilimumab and hypofractionated palliative radiation therapy is safe and well tolerated in patients with advanced salivary gland carcinomas.

2.2 Secondary Objective(s):

1. Evaluate the objective response rate according to RECIST 1.1
2. Determine overall and progression free survival

2.3 Exploratory Objective(s):

Collect tumor and blood for correlative studies

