6. STUDY DRUGS

The following investigational drugs will be provided. Premedications or medications used to treat infusion-related reactions should be sourced by the investigative sites if available and permitted by local regulations.

Product Description	Potency	Packaging/Appearance	Storage Conditions (per label)
(Nivolumab) Solution for Injection	100 mg (10 mg/mL)	10 mL/vial (5 or 10 vials/carton)	Store at 2° - 8°C. Protect from light and freezing.
Ipilimumab Solution for Injection	200 mg (5 mg/mL)	40 mL/vial (4 vials/carton)	Store at 2°- 8°C. Protect from light and freezing.

An investigational product, also known as investigational medicinal product in some regions, is defined a pharmaceutical form of an active substance or placebo being tested or used as a reference in a clinical study, including products already with a marketing authorization but used or assembled (formulated or packaged) differently than the authorized form, or used for an unauthorized indication, or when used to gain further information about the authorized form.

The investigational product should be stored in a secure area according to local regulations. It is the responsibility of the investigator to ensure that investigational product is only dispensed to study subjects. The investigational product must be dispensed only from the official study site by authorized personnel according to local regulations.

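### As worded, the Grade 3+ rate behind the radiation conclusion and the Grade 4+ count in 8.4 cover drug-related events only, so toxicity attributed to SBRT alone enters neither

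*Combined protocol and SAP*

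**What the plan says.** Section 2.1 gives the primary objective: "To demonstrate that nivolumab, ipilimumab and hypofractionated palliative radiation therapy is safe and well tolerated". SBRT is one of the three components. Two numbers serve this objective.

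- **Sample size determination** (repeated in the synopsis, Statistical Plan). Twenty patients are to estimate a 30% rate of Grade 3 or higher acute drug-related toxicity to within 20 points at 95% confidence, giving an upper bound of 50%. The text says this would reasonably "exclude a clinically significant increase in toxicity with the addition of radiation therapy", with the increase defined by that upper bound. The benchmark is 28%, from a phase I lung cancer study of the two drugs.
- **Section 8.4.** The rule is for the event that "the combination under study is deemed to have unacceptably high toxicities". What it counts is narrower: "Enrollment will be halted if more than 3 patients experience a Grade 4 or higher drug related toxicity". The window runs "during the trial treatment period or up to 30 days after the last investigational drug infusion".

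On attribution, 8.2 offers two categories, the first being "Related: There is a reasonable causal relationship between study drug administration and the AE" and the second its negation. Section 6 opens with "The following investigational drugs will be provided" and its table lists nivolumab and ipilimumab. Statistical Considerations says that adverse events will be graded and "their relationship to the experimental agents reported", without defining those agents. Section 7.1.2.1 asks for causality without saying against what.

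**The concern.** The conclusion concerns what happens when radiation is added, but the rate behind it is restricted to events attributed to the drugs. If an event is judged to come from SBRT alone, 8.2 provides only the not-related category, and the event leaves the numerator. A rate that cannot respond to that class of event cannot by itself rule out an increase that includes it.

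The same restriction affects trial conduct. The run-in DLT rule covers 6 patients for 12 weeks. For the other 14 of 20 (70%), 8.4 is the only numeric safety rule, and as worded it does not count these events. Committee review remains, but no criterion for them is stated.

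The class is not fanciful. The exclusion criteria bar certain target lesions in previously irradiated regions and cite carotid blow-out, fistula and airway risk.

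**Working it through.** **Step 1: which events each number counts**

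| Event attributed to | Grade 3+ rate (sample-size text) | Grade 4+ count (8.4) | Run-in DLT (5.1.2) |
|---|---|---|---|
| Drug only | counted | counted | can count |
| Drug and SBRT | counted | counted | can count |
| SBRT only | not counted | not counted | can count (6 patients, 12 weeks) |

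The DLT definition starts from any Grade 3 or higher toxicity, less listed exclusions, and does not require drug attribution.

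**Step 2: reproduce the plan's precision figure**

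Inputs from the sample-size text: n = 20, p = 0.30, 95% confidence.

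Wald half-width = 1.96 × √(p(1 − p)/n) = 1.96 × √(0.30 × 0.70/20) = 0.201. The interval is 9.9% to 50.1%, which matches the stated 20 points and 50%.

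**Step 3: add SBRT-only patients**

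The documents give no SBRT-only rate, so one or two patients are used purely as arithmetic. The starting point is 6 of 20 with drug-related Grade 3+ events (30%).

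| SBRT-only patients | Any-treatment rate | Wald 95% | Exact (Clopper-Pearson) 95% | Drug-related figure as planned |
|---|---|---|---|---|
| 0 | 6/20 = 30% | 9.9–50.1% | 11.9–54.3% | 30%, upper bound 50% |
| 1 | 7/20 = 35% | 14.1–55.9% | 15.4–59.2% | 30%, upper bound 50% |
| 2 | 8/20 = 40% | 18.5–61.5% | 19.1–63.9% | 30%, upper bound 50% |

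The last column does not move.

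**Step 4: the 8.4 count**

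Three patients with drug-related Grade 4+ events plus one with an SBRT-only Grade 4+ event make four patients with severe treatment toxicity. The rule's count is three, which is not more than 3, so it does not trigger.

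**Step 5: the probabilities stated in 8.4**

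Section 8.4 gives 80% and 91% at true rates of 20% and 25%, and 83% after 10 patients at 40%. Exact binomial tails for four or more patients are 58.9% and 77.5% (n = 20) and 61.8% (n = 10). For three or more they are 79.4%, 90.9% and 83.3%. The stated figures therefore match a threshold of three or more, not the one written. This is a separate inconsistency. It does not come from the choice of event, because relabelling the event leaves these probabilities unchanged at a given true rate.

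**The case against.** The strongest reply is that the lost class is narrow and the data are not lost.

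- Events related to both drug and SBRT count, so radiation that worsens drug toxicity would raise the drug-related rate.
- All adverse events are collected, and toxicities are tabulated by type.
- A study-procedure relationship of an SAE goes into the report narrative (section 8), study staff review adverse events weekly (section 3), and the oversight committees review adverse events and stopping rules.
- A drug-related rate is the right figure to set beside a benchmark for the drugs.

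All of this stands, and it limits the point. It does not bring an SBRT-only event into either number.

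A second reply is that attribution wording varies. Section 7.1.2.1 leaves causality open, and the experimental agents are undefined. The 8.4 window is also weak evidence about attribution: SBRT starts two weeks after first dosing, so the window covers it and fixes timing only. This too stands. A reader might infer that the protocol forbids counting SBRT toxicity as related. The documents do not go that far; they show only that the literal wording and the sole defined categories point to study drug.

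A reader might also infer that radiation toxicity goes unmonitored. That is not supported. Section 5.1.2 names it within adverse-event monitoring of the run-in patients, and collection covers all events.

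**Conclusion.** The concern holds on the literal text. Toxicity attributed to SBRT alone enters neither the Grade 3+ rate nor the 8.4 count, so the drug-related rate cannot by itself exclude a toxicity increase from adding radiation. The gap lies in what these two numbers measure, not in data collection. It should be fixed.

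The size is unknown and may be small. A reader might assume rates and infer a large effect on 8.4. With independent 10% drug-related and 10% SBRT-only Grade 4+ rates, the chance of more than 3 of 20 would be 13.3% on the drug-related count and 54.4% if all treatment-related events counted. With SBRT-only rates of 5% and 15%, the second figure would be 32.8% and 72.6%. Neither the rates nor the independence comes from the documents, so these figures do not measure the problem.

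The conclusion rests on drug-related being read as written and on 8.2 being the operative causality definition.

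**What to change.** 1. **Attribution.** In 8.2, record attribution to SBRT as well as to study drug for each adverse event. Define the experimental agents in Statistical Considerations to match.
2. **Radiation conclusion.** Report the Grade 3+ acute toxicity rate related to any study treatment (nivolumab, ipilimumab or SBRT) with its 95% interval, and base any conclusion about adding radiation on it. State in advance the upper bound against which it will be read, and say that the 30%/50% planning precision applies to the drug-related rate only. Keep the drug-related rate for comparison with the drug benchmark. Otherwise, limit the conclusion in the synopsis and sample-size text to drug-related toxicity.
3. **Section 8.4.** Reconcile the event counted with the stated purpose of guarding the combination. Which event applies is for the sponsor to decide. If it is widened, restate which true rates are considered acceptable and unacceptable for it.

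The cost is one field on the adverse-event form and wording in the synopsis, 8.2, 8.4 and the statistical section. No extra patients are needed. Planning the wider rate to a 50% Wald upper bound would be a different design and is not proposed: n = 1.96² × p(1 − p)/(0.50 − p)² gives 38.8, so 39 patients at 35%, and 92.2, so 93 at 40%. The downside is a somewhat higher counted rate and upper bound and, if 8.4 is widened, a higher chance of halting enrollment, by an amount the documents do not allow to be calculated.

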4. INVESTIGATIONAL PLAN/STUDY DESIGN

4.1 Study Design Overview

This study will be carried out as a single institution, single arm phase I/II unblinded trial. A maximum of 20 patients will be enrolled. Each patient will be treated with nivolumab, ipilimumab and stereotactic body radiation therapy. Nivolumab will be continued for a total of 12 cycles, unless evidence of unacceptable toxicity, disease progression or withdrawal of patient consent were to occur.

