5.1.2 Definition of DLT

Dose-limiting toxicities (DLTs) will be evaluated during the run-in phase consisting of the first 6 patients enrolled in this trial. The period for evaluating DLTs will be from the time of first administration of nivolumab and ipilimumab until 12 weeks. Adverse event monitoring will continue for these subjects throughout the course of their treatment as outlined in the Schedule of Study Assessments, these adverse events will include potential XRT related toxicities. Subjects who do not remain on the study up to this time for reasons other than DLT will be replaced with another subject. Grading of DLTs will follow the guidelines provided in the Common Terminology Criteria for Adverse Events (CTCAE) version 5.0.

A DLT will be defined as any Grade 3 or higher toxicity that occurs during the DLT evaluation period. Toxicity that is clearly and directly related to the primary disease or to another etiology is excluded from this definition. The following will be DLTs:

- Any Grade 4 irAE
- Any \geq Grade 3 colitis
- Any Grade 3 or 4 noninfectious pneumonitis irrespective of duration

- Any Grade 2 pneumonitis that does not resolve to \leq Grade 1 within 3 days of the initiation of maximal supportive care
- Any Grade 3 irAE, excluding colitis or pneumonitis, that does not downgrade to Grade 2 within 3 days after onset of the event despite optimal medical management including systemic corticosteroids or does not downgrade to \leq Grade 1 or baseline within 14 days
- Liver transaminase elevation $> 8 \times$ ULN or total bilirubin $> 5 \times$ ULN
- Any \geq Grade 3 non-irAE, except for the exclusions listed below
 - Grade 3 fatigue lasting \leq 7 days
 - Grade 3 endocrine disorder (thyroid, pituitary, and/or adrenal insufficiency) that is managed with or without systemic corticosteroid therapy and/or hormone replacement therapy and the subject is asymptomatic
 - Grade 3 inflammatory reaction attributed to a local antitumor response (e.g., inflammatory reaction at sites of metastatic disease, lymph nodes, etc.)
 - Concurrent vitiligo or alopecia of any AE grade
 - Grade 3 infusion-related reaction (first occurrence and in the absence of steroid prophylaxis) that resolves within 6 hours with appropriate clinical management

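### After the six-patient run-in, no numeric trial-level trigger uses the Grade 3+ toxicity rate on which the sample size is planned; Section 8.4 counts only Grade 4+ events

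*Combined protocol and SAP*

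**What the plan says.** Section 8.4 introduces its rule with the words "In keeping with the study primary endpoint, a stopping rule will be implemented", and then sets it: "Enrollment will be halted if more than 3 patients experience a Grade 4 or higher drug related toxicity". Events count "during the trial treatment period or up to 30 days after the last investigational drug infusion".

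Under Statistical Considerations, "Safety and tolerability is the primary endpoint of this study"; no grade or rate is attached to that sentence. The grade appears in Sample size determination (repeated in the Synopsis, Statistical Plan), where 20 patients are said to suffice to "estimate grade 3 or higher acute drug related toxicity rate of 30% with a confidence interval of 20" percent. The resulting upper bound of 50% is what the plan uses to exclude a clinically significant increase in toxicity.

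The run-in is the one trial-level place where Grade 3 events count: "Dose-limiting toxicities (DLTs) will be evaluated during the run-in phase consisting of the first 6 patients enrolled in this trial", over 12 weeks. Enrolment pauses for that review (Section 4.2). If the DLT threshold is met, Section 5.1.1 gives another schedule for the remaining 14 patients, however many DLTs there were.

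**The concern.** The rule that can halt enrolment watches a more severe and rarer outcome than the one the trial is sized to judge. From patient 7 onward, Grade 3 events do not count toward any numeric trial-level trigger on either schedule. If most of the excess toxicity is Grade 3, enrolment could continue to 20 while the Grade 3+ rate runs well above the planned 30%, with no pre-specified point at which the DSMC must look at it.

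**Working it through.** **Inputs.** N = 20 (Section 4.1: "A maximum of 20 patients will be enrolled"). The rule is more than 3, that is 4 or more, patients with Grade 4+ drug-related toxicity (8.4). The planned Grade 3+ rate is 30% with upper bound 50% (Sample size determination). The share of Grade 3+ patients who reach Grade 4+ is not given, so 10% to 50% is assumed here.

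**The plan's own figures.**
- Precision: 1.96 × √(0.30 × 0.70 / 20) = 0.201, so 30% plus 20 points is 50%. This reproduces.
- Stopping rule: Section 8.4 states 80% (true rate 20%), 91% (25%) and 83% (40%, first 10 patients). Exact binomial tails for 4 or more are 58.9%, 77.5% and 61.8%. For 3 or more they are 79.4%, 90.9% and 83.3%. The stated figures therefore match 3 or more and not the wording. The two must be reconciled, and both readings are shown below.

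**Chance that 8.4 reaches its count.** With true Grade 3+ rate g and Grade 4+ share s, the Grade 4+ rate is p = g × s, and the probability is P(X ≥ 4), X ~ Binomial(20, p). For example, g = 60% and s = 20% give p = 0.12 and P = 0.213.

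| True Grade 3+ rate and reading | s = 10% | 20% | 30% | 40% | 50% |
|---|---|---|---|---|---|
| 50%, 4 or more of 20 | 2% | 13% | 35% | 59% | 77% |
| 60%, 4 or more of 20 | 3% | 21% | 50% | 74% | 89% |
| 70%, 4 or more of 20 | 5% | 30% | 63% | 85% | 96% |
| 60%, 3 or more of 20 | 11% | 44% | 73% | 89% | 96% |
| 60%, 4 or more by patient 19 | 2% | 19% | 45% | 70% | 87% |

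The last row matters for halting enrolment, because a count reached at patient 20 comes when nobody is left to enrol. All rows hold the rate constant and treat each outcome as known at once. The event window runs through treatment plus 30 days, so late events would make the rule slower in practice.

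**Run-in.** If the DLT rate is taken as equal to a Grade 3+ rate of 60%, then P(2 or more of 6) = 96% and P(more than 2 of 6) = 82%. Both are shown because Section 5.1.1 says 2 or more, while the Synopsis and Section 4.2 say more than 2; these passages must be reconciled. The equality is rough, since Section 5.1.2 excludes several Grade 3 events from the DLT definition.

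**Why the existing count cannot simply be moved to Grade 3+.** At the planned 30%, P(X ≥ 4 of 20) = 89%, so such a rule would nearly always trigger when toxicity is as expected.

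**An added trigger.** Take 6 or more of the first 10, or 10 or more at any time up to patient 19. The probability is P(X₁₀ ≥ 6) + Σ P(X₁₀ = x) × P(Y₉ ≥ 10 − x), summed over x = 0 to 5, where X₁₀ counts events in the first 10 patients and Y₉ in the next 9. At 60% this is 0.633 + 0.212 = 0.845.

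| True Grade 3+ rate | First 10 only | By patient 19 |
|---|---|---|
| 30% | 5% | 6% |
| 50% | 38% | 56% |
| 60% | 63% | 84% |
| 70% | 85% | 97% |

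**The case against.** Several points on the other side stand.

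- A reader might infer that 8.4 contradicts the primary endpoint. It does not: the endpoint is safety and tolerability without a grade, and a rule on life-threatening events can be in keeping with it. The mismatch is between the stopping rule and the sample-size basis.
- A reader might treat 50% as the plan's halting limit. The plan gives it only as the upper confidence bound when 30% is observed.
- A reader might infer that nothing responds to Grade 3 toxicity after patient 6. Section 5.1.3.1 holds drug for most Grade 3 or higher drug-related events, and Section 5.1.3.3 discontinues on recurrence of a Grade 3 treatment-related event. These act on individuals. The study team also meets weekly on adverse events (Section 3), and the committees in Section 9 review adverse events and must approve continuation as applicable, but no Grade 3+ threshold is stated for them.
- The existing rule may do the work. At a 40% or 50% share and a true 60%, it reaches its count 74% or 89% of the time.
- A constant 60% over 20 patients is an assumption. The run-in would probably trigger at that rate, and the other 14 would then be on another schedule, with a rate that the documents do not predict.

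These points limit the size of the problem. They do not supply a numeric trial-level check on the Grade 3+ rate.

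**Conclusion.** The gap is real and is best treated as a low-cost improvement, not as an error that undermines the trial. After the run-in, no numeric trial-level trigger uses the rate on which the sample size rests. Its practical size is uncertain because the Grade 4+ share is unknown: at a true Grade 3+ rate of 60%, the chance of reaching the 8.4 count runs from 3% to 89% as the share goes from 10% to 50% (11% to 96% if the rule means 3 or more). Protection is weak at shares up to about 20% and substantial from about 40%. The documents do not support the claim that a high Grade 3+ rate would usually go unchecked. These figures assume independent patients, a constant rate and immediate knowledge of outcomes.

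**What to change.** Keep the Grade 4+ limb. Add to 8.4 a trigger for DSMC review, not an automatic stop, on Grade 3 or higher drug-related toxicity, with a stated event window that matches the acute measure in the sample-size text, which gives none. As an illustration: review before further enrolment if 6 or more of the first 10 patients, or 10 or more patients at any time before enrolment closes, have such an event. These are observed rates of 60% at the first look and 50% of the full 20. The study team and DSMC should set the final numbers.

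State the operating characteristics while enrolment is still open (by patient 19 in the table above), not at patient 20, and recompute them once the window and reporting delay are fixed. In the same edit, reconcile the 8.4 threshold with its stated probabilities.

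The cost is a short protocol amendment; the events are already graded and reviewed weekly. The downside is about a 6% chance of an unneeded review if the true rate is the planned 30%.
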